All the subjects will give their written informed consent before inclusion in the study. The present study was approved by the ethical committee for human research of Instituto Tecnológico y de Estudios Superiores de Occidente (ITESO) (0001DRC) and was performed in accordance with the ethical standards laid down in the 1964 Declaration of Helsinki and its later amendments.

Randomization:

Participants will be randomly assigned, using a computerized random number generator (STATA software), to one of two treatments: nutrigenetic diet or conventional diet. Randomization will be stratified according to age, BMI and sex. The allocation ratio will be 1:1

Genotyping of gene polymorphisms related to dyslipidemias in Mexicans

Based on a previous systematic review, 11 gene polymorphisms associated with dyslipidemias in Mexicans were identified and were taken into account to perform genotyping in the study population.

The gene polymorphisms under study are:

ABCA1 rs9282541

PPARG rs1801282
LIPC rs1800588
CETP rs708272
LPL rs13702
FABP2 rs1799883
APOA5 rs662799
APOC3 rs5128
APOA1 rs670
APOE rs429358 and rs7412

A blood sample will be taken from the participants, then DNA will be extracted from leucocytes using a commercial extraction kit (High Pure PCR Template Preparation kit, *Roche*). Polymorphisms will be detected by a real-time RT-PCR system using allelic discrimination (TaqMan ®) in a 96-well format and will be read by a Roche LightCycler 96 system (Roche, Mannheim, Germany). PCR conditions will 40 cycles of amplification at 95°C for 10 min, and annealing/ extension at 60°C for 60 seconds.

The experimental phase will last 8 weeks.

Participants will attend 3 three visits to the clinical unit (Centro Universitario de Ciencias de la Salud, Universidad de Guadalajara): on the starting day of the intervention period (baseline), after 4 weeks (1st month) and after 8 weeks of intervention (final visit). Participants will also receive remote nutritional counseling every 15 days (5 consultations in total).

Anthropometric measurements

Anthropometric parameters will be measured three times during intervention period (baseline, week 4, week 8).

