CONVENTIONAL DIET: weekly, personalized meal plans (menus) will be provided every 2 weeks, prepared based on the anthropometric needs of the patients, with a caloric reduction (-500 kcal). These weekly menus (Sunday to Monday) consist of 5 meal times (breakfast, snack, lunch, snack and dinner). The target macronutrient composition of this treatment is: 50% carbohydrates, 20% proteins and 30% fats in accordance with the recommendations made by the WHO (World Health Organization), the AHA (American heart association) and the NOM (Official Mexican Standards) for the treatment of obesity and dyslipidemias.

The percentages of macronutrients and fatty acids of all the menus will be adjusted using Foodprocessor nutrition software ®

All participants will receive remote (virtual) nutritional counseling every 15 days (5 individual sessions) with the dietitian to explain the diet, solve doubts, provide nutrition strategies and to complete the nutritional medical history, which includes physical activity record (IPAQ- short version) and questionnaires of frequency of food consumption to monitor adherence to nutritional intervention. Records will be analyzed with a computer-based data evaluation system (Foodprocessor nutrition software ®). National composition food tables will be also used as reference.

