Official title:

**EFFECT OF A NUTRIGENETIC INTERVENTION ON BLOOD LIPID MARKERS AND BODY
COMPOSITION OF ADULTS WITH OVERWEIGHT AND OBESITY**

STATISTICAL ANALYSIS PLAN

September , 30, 2021.

Statistical analysis plan

Sample size was calculated *a priori*, considering the mean difference in total cholesterol between study groups as primary outcome variable (De Luis et al. 2017). GPower V3.1.9.4 software was used for the pertinent calculations. A power contemplated: 95%, and significance α : 0.5%. The effect size: 0.9772364. One-tailed, to analyze differences with the t-test. 30% loss to follow-up was considered. A minimum of 24 participants per treatment were required. The aim was to recruit 50 subjects per treatment

All the data will be analyzed using SPSS for MAC, version 26.0 software package (SPSS Inc. Chicago, IL). Parametric tests will be applied for quantitative variables with normal distribution, and non-parametric tests for qualitative and quantitative variables with abnormal distributions. The Kolmogorov–Smirnov test will be used to determine variable distribution. The results will be expressed as average \pm standard deviation.

For each treatment group, all markers will be tested using Student's paired-sample t test for possible difference between values achieved at baseline (visit 1) and 1st month (4 weeks) and visit 3 (final point, 8 weeks), respectively. Student's two independent- samples t tests will be also performed to find possible difference regarding these markers between treatments Nutrigenetic diet and Conventional diet. Furthermore, a mixed models approach including repeated-measures modeling will be utilized to find possible significant effects of the treatment effect at baseline on treatment effect after two subsequent clinical visits. This model will considerate confounders.

Categorical variables will be analyzed with the chi-square test, with Yates correction as necessary, and Fisher's test.

The statistical analysis to evaluate the gene-diet interaction was a univariate ANCOVA.

A Chi square test will be used to evaluate the Hardy–Weinberg equilibrium.

A P- value b 0.05 was considered significant.

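### The week-8 diet comparison should rest on the already planned mixed model in all randomised participants, because the t-tests compare completers while 30% loss is allowed for

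*SAP*

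**What the plan says.** The SAP sizes the trial by "considering the mean difference in total cholesterol between study groups as primary outcome variable", using a one-tailed t-test, and adds that "30% loss to follow-up was considered". It gives a minimum of 24 per arm and a recruitment aim of 50.

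For the analysis, the SAP plans paired t-tests within each arm (baseline against week 4, and baseline against week 8). For the diets it says "Student's two independent- samples t tests will be also performed to find possible difference regarding these markers between treatments Nutrigenetic diet and Conventional diet". That sentence names neither the visit nor whether values or changes are compared. A repeated-measures mixed model with confounders follows as a further analysis. Its stated target, the influence of a baseline treatment effect on later treatment effects, is not a week-8 contrast between diets.

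The Protocol schedules clinic visits "on the starting day of the intervention period (baseline), after 4 weeks (1st month) and after 8 weeks of intervention (final visit", with blood taken at all three. Under Diets, the counselling sessions include "questionnaires of frequency of food consumption to monitor adherence to nutritional intervention".

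Neither document defines an analysis population, states that participants are analysed as assigned, gives a rule for missing values, or says whether outcomes are still measured in someone who stops the diet.

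**The concern.** A between-diet t-test at week 8 can use only those who have a week-8 value. If 30% are lost, it compares about 35 completers with 35 completers, and randomisation no longer guarantees that they are alike. Suppose participants who respond poorly leave one arm, while departures from the other arm are unrelated to response. The first arm then looks better at week 8 even when the diets are equal. Equal dropout percentages do not prevent this, because what matters is who leaves.

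The trial collects two earlier measurements that carry information about those who leave after week 4. The mixed model could use them, but an analyst following the SAP as written could report the t-test as the main result. The fit is not specified either: a repeated-measures general linear model in SPSS would delete incomplete cases and so share the problem.

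**Working it through.** **Inputs from the documents**

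- SAP: "The effect size: 0.9772364", one-tailed t-test, 95% power, 30% loss, 24 per arm as minimum, 50 per arm as aim.
- Protocol, Randomization: 1:1 allocation.
- Protocol, Biochemical measurements: baseline, week 4 and week 8.

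**Assumptions (not in the documents)**

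- Total cholesterol SD of 1 at each visit.
- Correlation 0.7 of baseline with each later visit, and 0.8 between weeks 4 and 8.
- 50 per arm, 30% lost in each arm, all after week 4.
- No true diet difference; one-sided 5% test.

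**Step 1. The plan's own figure.** The normal approximation is n = 2(1.645 + 1.645)²/0.9772² = 21.65/0.955 = 22.7, so 23 per arm. The exact noncentral t gives 24 (power 95.45%), which reproduces the SAP at one-sided 5%. The SAP prints "A power contemplated: 95%, and significance α : 0.5" (per cent), but that level would need 40 per arm. The 24 therefore rests on 5%, in line with the later statement that a P value of "0.05 was considered significant". The misprint is a separate matter.

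**Step 2. What 30% loss does to power.** 24/(1 − 0.3) = 34.3, so 35 per arm; the 24 is the number before loss. At the aim of 50, 50 × 0.7 = 35 remain, with power 99.2% at one-sided 5%. Power is covered, which leaves bias.

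**Step 3. Standard errors when loss is random.**

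- Week-8 t-test: √(2/35) = 0.239.
- t-test on change: variance of change = 2(1 − 0.7) = 0.6; √(2 × 0.6/35) = 0.185.
- Baseline-adjusted completers: √(2 × (1 − 0.49)/35) = 0.171.
- Likelihood fit using all visits: given baseline, the week-4 and week-8 variances are 0.51 and their covariance is 0.8 − 0.49 = 0.31. The part of week 8 explained by week 4 is 0.31²/0.51 = 0.188, leaving 0.322. SE = √(2 × (0.322/35 + 0.188/50)) = 0.161.

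Most of the gain comes from using baseline (0.239 to 0.171). Week 4 adds about 6% (0.161/0.171 = 0.94).

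**Step 4. Bias under selective dropout.** This was simulated with 4,000 trials per scenario. Dropout depended on week-4 change in the nutrigenetic arm only, with log-odds of 1.0 or 1.5 per SD, and was random in the conventional arm. All biases favour the nutrigenetic diet.

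| Analysis | Bias (SD) | False-positive rate |
|---|---|---|
| Week-8 t-test | about 0.03 to 0.04 | about 7% |
| t-test on change | about 0.12 to 0.17 | about 17% to 23% |
| Likelihood fit, all visits | below 0.01 | not inflated by bias |

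Check by 1 − Φ(1.645 − bias/SE):

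- Week-8 t-test: 0.04/0.24 = 0.167, so 1 − Φ(1.478) = 7.0%.
- t-test on change: 0.17/0.185 = 0.919, so 1 − Φ(0.726) = 23%. At 0.12 it gives 16%, close to the simulated lower end.

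**Step 5. Other dropout patterns.** With both arms selective but unequal (log-odds 1.5 and 1.0), false-positive rates are about 5% to 8% across the week-8 t-test, the change t-test and a baseline-adjusted completers' analysis. With equal selection in both arms, bias is near zero and the rate is about 5%.

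**The case against.** The strongest case against has four parts.

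- **The plan does use week-4 data.** The paired tests compare baseline with week 4, so a participant lost after week 4 still contributes there. A reader might infer that the SAP throws these values away; it does not. It remains true that a between-diet t-test at week 8 makes no use of them.
- **The large error rates need tests that the SAP does not name.** The between-diet sentence reads most plainly as a comparison of values, for which the inflation is from 5% to about 7%. The 17% to 23% needs a t-test on change. The SAP's only ANCOVA is for gene-diet interaction. This stands and limits the size of the point.
- **One-arm selection is an extreme case.** Participants are masked, and both arms have the same energy reduction, meal pattern and counselling schedule. Nothing says that participants learn their week-4 cholesterol. This makes similar dropout in the two arms plausible, but it does not exclude a difference, because the menus differ in composition.
- **The remedy's near-zero bias follows from the set-up.** All simulated loss came after week 4 and depended on observed values only. This also stands, so the benefit is claimed for that kind of loss alone.

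A reader might also infer that anyone who stops the diet is withdrawn. The documents do not say so. The Protocol states the three visits without any condition on adherence, and the wording of the final visit reads as a time point. Someone who stopped the diet but attended at week 8 would be in the t-test. On this the documents are silent, which calls for a clarification and is not evidence of a withdrawal rule.

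**Conclusion.** The point holds as a weakness in the choice of main analysis. The SAP allows for substantial loss, compares completers, and leaves the analysis that handles incomplete follow-up better as an addition with an unclear target.

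For the test most plainly described, the size is modest. A bias of 0.04 SD is about 4% of the planned effect (0.04/0.977), with a false-positive rate of about 7%. If the analyst tests change, 0.17 SD is about 17% of it (0.17/0.977). If dropout works the same way in both arms, there is essentially no bias. These figures rest on the assumed correlations, on loss after week 4, and on selection in one arm; 30% is itself a planning allowance.

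A reader might conclude that the trial will be biased, or that its false-positive rate will be several times nominal. The documents support neither: they give no information on the dropout mechanism, and bias needs dropout that is both related to response and different between arms. The gain in precision, a SE of about 0.16 against 0.24 SD, does not depend on selective dropout and is a reason for the change in its own right.

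**What to change.** **SAP.** Name the mixed model as the primary week-8 comparison of the diets. Specify that:

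- it includes all randomised participants in the group assigned;
- it is fitted by likelihood to every available baseline, week-4 and week-8 value;
- baseline is accounted for, for example by one baseline mean common to both diets;
- the reported effect is the diet difference in total cholesterol at week 8;
- missing values are assumed missing at random.

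Keep the t-tests as supportive analyses.

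**Protocol (clarification).** State that week-4 and week-8 measurements are taken in every randomised participant who still consents, whether or not they continue the diet or counselling.

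**Cost.** The visits, blood tests and model are already planned, so the cost is SAP wording, a sentence in the Protocol and a little more analysis work. The downside is reliance on the missing-at-random assumption. The model does not correct losses before week 4 that depend on unobserved outcomes, or later dropout that is not at random; continued measurement is what limits those.

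### The test and effect scale for skewed secondary markers are data-driven and contradictory; the power at stake lies in raw-scale and unadjusted analysis rather than in the normality pre-test

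*SAP*

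**What the plan says.** The SAP's second paragraph, on software and choice of tests, sets a general rule: "Parametric tests will be applied for quantitative variables with normal distribution", and "non-parametric tests for qualitative and quantitative variables with abnormal distributions". The sorting is done by a pre-test: "The Kolmogorov–Smirnov test will be used to determine variable distribution". The SAP gives no level for this test and does not say whether Lilliefors or plain critical values apply. Nor does it say whether the test is run per arm, per visit, on changes or on residuals. No rank test is named and no transformation is mentioned. On reporting, the same paragraph says: "The results will be expressed as average", followed by the standard deviation, with no exception.

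The third paragraph then says: "For each treatment group, all markers will be tested using Student's paired-sample t test". For the between-arm comparison, independent "samples t tests will be also performed to find possible difference regarding these markers between treatments". Neither sentence carries a normality condition. A repeated-measures mixed model with unnamed confounders follows. It is not tied to the pre-test, and its scale is not stated.

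The Protocol's hypothesis covers plasma lipids and inflammatory markers. Its list of dependent variables and its section on biochemical measurements include triglycerides, VLDL, CRP, insulin, HOMA-IR, IL-1, IL-6, IL-10 and TNF-alpha, measured at baseline, week 4 and week 8.

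**The concern.** Under the second paragraph, a skewed marker gets a raw-scale t-test or a rank test according to how the sample falls. Under the third, it gets a raw-scale t-test regardless. These routes answer different questions: a difference in arithmetic means, or a shift in ranks. If ranks are used, the reported mean and SD do not describe what was tested.

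The markers exposed to this are positive quantities that are plausibly right-skewed, and they carry the inflammatory part and some of the lipid part of the hypothesis. At stake are a choice of analysis that depends on the outcome data, an effect scale that may differ between markers for no planned reason, and lost power where a skewed marker is analysed raw or without its baseline.

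**Working it through.** **Group sizes.** From the SAP: effect size 0.9772364, one-tailed, power 95%, minimum 24 per arm, 30% loss, target 50 per arm. Two-sample t power uses noncentrality d × √(n/2). With n = 24, 0.9772364 × √12 = 3.385 on 46 df. At one-tailed 5% the power is 95.4%, so the plan's 24 is reproduced. The normal approximation, 2 × (1.645 + 1.645)² / 0.9772² = 22.7, gives 23. The printed alpha of 0.5% would need 40 per arm; that is a separate matter. The target leaves 50 × 0.7 = 35 completers, so 24, 35 and 50 per arm were examined.

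**Assumptions.** The documents give no SDs or distributions for these markers. I assumed lognormal data with log-SD 0.2 (cholesterol-like), 0.5 (triglyceride-like), 0.7 (cytokine-like) and 1.0 (CRP-like), and two-sided 5% tests. The log-scale effect was set so that a log t-test has 80% power (0.83, 0.68 and 0.57 log-SD at 24, 35 and 50 per arm). The two-stage rule was taken as Mann-Whitney if either arm is flagged at 5%, otherwise a raw t-test. Each cell has 10,000 simulated trials; the Monte Carlo standard error is √(0.8 × 0.2 / 10,000) = 0.4 points.

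**Results at 35 per arm**

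| Log-SD | One arm flagged: Lilliefors / plain | Raw t | Mann-Whitney | Two-stage: Lilliefors / plain | Log t |
|---|---|---|---|---|---|
| 0.2 | 13% / 0.1% | 79.8% | 78.2% | 80.0% / 79.8% | 80.5% |
| 0.5 | 54% / 5% | 75.4% | 77.6% | 77.9% / 76.6% | 80.0% |
| 0.7 | 80% / 20% | 71.3% | 77.9% | 78.0% / 76.5% | 80.0% |
| 1.0 | 96% / 54% | 62.1% | 78.5% | 78.5% / 78.2% | 80.6% |

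**Is the sorting reliable?** Not for moderate skew. At 24 per arm, Lilliefors flags 10%, 40%, 63% and 86% of single arms for the four log-SDs; plain critical values flag about 0%, 2%, 9% and 29%. If the pre-test is run per arm with flag probability p, the arms disagree with probability 2p(1 − p). At 35 per arm this is 2 × 0.55 × 0.45 = 0.50 at log-SD 0.5, 2 × 0.80 × 0.20 = 0.32 at 0.7, and 2 × 0.96 × 0.04 = 0.08 at 1.0.

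**What does the pre-test cost?** Log t minus the two-stage rule at 35 per arm, for log-SD 0.5 to 1.0, is 2.0 to 2.1 points with Lilliefors and 2.4 to 3.5 with plain critical values. The worst cell is 24 per arm, log-SD 0.7, plain critical values: 80.2 − 75.0 = 5.2 points. Type I error of the two-stage rule is 4.7% to 5.8% throughout. At log-SD 0.2 the loss is below 1 point.

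**What does a raw t-test for every marker cost?** At 35 per arm: 80.0 − 75.4 = 4.6 points (log-SD 0.5), 80.0 − 71.3 = 8.7 (0.7) and 80.6 − 62.1 = 18.5 (1.0). With a smaller effect of 0.6 log-SD, the loss is about 5 to 17 points.

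**What does baseline adjustment add?** It divides the standardised effect by √(1 − ρ²). At 35 per arm and 0.6 log-SD, the unadjusted log t-test has noncentrality 0.6 × √17.5 = 2.51 and power 70%. With ρ = 0.5 this becomes 2.51 / √0.75 = 2.90 and 81%; with ρ = 0.7, 2.51 / √0.51 = 3.51 and 93%. The gain is about 11 to 23 points. At 24 per arm and 0.83 log-SD, power rises from 80% to 90% (ρ = 0.5) and 97.5% (ρ = 0.7).

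**Does adjustment on the raw scale suffice?** No. At 35 per arm, 0.6 log-SD and ρ from 0.5 to 0.7, a raw-scale baseline-adjusted model has 58% to 70% power at log-SD 1.0, against 81% to 93% on the log scale. At log-SD 0.5 the figures are 74% to 88% and 82% to 94%.

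**The case against.** The strongest reply is that the pre-test does little harm. Strong skew is mostly detected and sent to a rank test nearly as efficient as a log t-test; missed skew is mostly mild, where a raw t-test loses little. With Lilliefors critical values, that stands. A reader might set an unadjusted rank test (66% to 69% at 35 per arm and 0.6 log-SD) beside a baseline-adjusted log model (80% to 93%) and blame the pre-test for the gap. That would be wrong: the unadjusted log t-test has 68% to 70%, so nearly all of the gap is baseline adjustment.

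A reader might also infer that the two arms would be classified differently in about half of trials. That holds only near log-SD 0.5 and only for per-arm testing, which the SAP does not specify. Tested once on pooled data, a marker cannot be split between arms, and detection at log-SD 0.5 is about 84% to 87% with 70 subjects.

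Nor do the documents support saying that rank methods can neither adjust nor give an estimate. Rank ANCOVA, the van Elteren test and the Hodges-Lehmann shift exist, and the SAP names no rank test. The mixed model may supply some adjustment, and it cannot be called wrongly scaled when no scale is stated.

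Finally, the t-test paragraph could be read as the parametric branch of the general rule. That is possible, but its wording covers all markers without condition, so the two paragraphs still need reconciling. The reporting mismatch remains on either reading.

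**Conclusion.** The point holds for the secondary markers. The SAP gives two incompatible routes for a skewed marker and one summary that does not suit rank testing, so test and effect scale are left to the data and to the analyst's reading.

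The pre-test's own power cost is small (about 1 to 5 points) and error control is sound; its harm is arbitrary selection. Material losses arise if skewed markers are analysed raw (about 5 to 18 points for a t-test at 35 per arm) and, as a separate matter, if the baseline is not used (about 10 to 25 points). Total cholesterol, on which the sample size rests, is hardly touched by the choice of scale, though baseline adjustment would help it too.

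The sizes rest on assumed lognormal markers with log-SD 0.5 to 1.0 and baseline correlations of 0.5 to 0.7, none of which the documents supply. The contradiction rests on the SAP text alone. This should be corrected, but it does not threaten the primary comparison.

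**What to change.** Delete the Kolmogorov-Smirnov rule and the unconditional between-arm t-tests. Pre-specify one baseline-adjusted model for each marker:

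- original scale for total cholesterol, LDL-C, HDL-C, glucose and anthropometry;
- natural-log scale for triglycerides, VLDL, CRP, insulin, HOMA-IR, IL-1, IL-6, IL-10 and TNF-alpha.

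The mixed model already planned can serve, once its scale and the baseline covariate are written down. Check residual plots, report adjusted mean differences or geometric mean ratios with 95% CI, and keep a named rank test as a sensitivity analysis. If within-arm paired comparisons are kept, run them on the same scale as the marker's model.

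The cost is SAP wording; no data collection changes. There are two small drawbacks: logged markers are reported as ratios, and values below an assay limit need a handling rule fixed in advance.

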Official title:

**EFFECT OF A NUTRIGENETIC INTERVENTION ON BLOOD LIPID MARKERS AND BODY
COMPOSITION OF ADULTS WITH OVERWEIGHT AND OBESITY**

STUDY PROTOCOL

September, 30, 2021

“EFFECT OF A NUTRIGENETIC INTERVENTION ON BLOOD LIPID MARKERS AND BODY COMPOSITION IN OVERWEIGHT AND OBESO ADULTS”

STUDY PROTOCOL

- **Hypothesis**

A nutrigenetic diet administered to adults with genetic polymorphisms related to obesity and dyslipidemias will provide a greater decrease in plasma lipids, inflammatory markers and improvement in body composition, compared to the administration of a standard diet.

- **Objective:**

To evaluate the effect of a nutrigenetic intervention on blood biochemical and inflammatory markers and body composition in overweight and obese adults.

- **Design:**

Study type: Interventional

- **Interventional Study Model:**

Randomized controlled clinical trial, parallel assignment, with 2 study groups.

Two arms.

Masking: Single (participant).

Intervention period: 8 weeks.

Research site: ITESO and Centro Universitario de Ciencias de la Salud, Universidad de Guadalajara, México.

- **Methods:**

Participants

The recruitment of the population was carried out from the month of May to the month of September of the current year in the CD of Guadalajara, Jalisco and neighboring municipalities. The dissemination of informative flyers was done digitally through various social networks and also verbally.

Inclusion criteria

-Men and women

-18-50 years old

-Mexican- mexican ancestry (3 generations at least)

-Live in Guadalajara, Jalisco or metropolitan area

-Being overweight or obese (BMI 25>40)

-Waist circumference:

Women: > 80 cm

Men: > 94 cm

-Availability to attend virtual nutritional consultations.

Exclusion criteria

- Not meeting the inclusion criteria
- Pregnancy or breastfeeding
- Gastrointestinal disorders
- Endocrinopathies
- Cardiovascular events
- Diagnosed psychiatric illnesses
- Diagnosed diabetes
- Take lipid-lowering drugs
- Autoimmune diseases
- Covid +

Dependent variables:

Height, body weight, BMI, total body fat, fat mass index, skeletal muscle mass, visceral fat, waist circumference, hip circumference, total cholesterol (TC), LDL-cholesterol (LDL-C), HDL-cholesterol (HDL-C), triglycerides, C-reactive protein (CRP), glucose and insulin, total energy, macronutrients, micronutrients.

Independent variables:

Sex, age, presence or absence of polymorphisms, and intervention group.

INTERVENTION

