Measurements will be performed after 8- 10 hours of fasting. Height measurements will be taken using a stadiometer (Rochester Clinical Research, Rochester, NY, USA). Tetrapolar electrical bioimpedance will be used to assess weight and body composition (InBody 120 body composition analyser; Biospace, Seoul, Korea). BMI will be calculated as weight in kilograms divided by height in meters squared (kg/m²). The waist (narrowest diameter between the xiphoid process and the iliac crest) and hip (the widest diameter over the greater trochanters) circumferences will be measured (Lufkin anthropometric tape W606PM). Blood pressure will be measured, while seated, in the non- dominant arm using a digital automatic BP monitor (Model M3 Intelligence, Omron, Healthcare Company, Limited).

Biochemical measurements

Biochemical measurements will be performed three times during intervention period (baseline, week 4, week 8).

Venous blood samples will be taken after overnight fasting, and serum will be immediately separated by centrifugation. Measurements of total cholesterol, triglycerides, high-density lipoprotein cholesterol (HDL-C), glucose, very low density lipoprotein (VLDL) and C- reactive

protein will be performed using a Vitros-250 dry chemistry analyser (Ortho- Clinical Diagnostics, Johnson & Johnson Services, Inc., Rochester, NY, USA). LDL-C levels will be calculated using the Friedewald formula. The homeostatic model assessment of insulin resistance (HOMA-IR) will be calculated as described by Matthews et al. (1985). Insulin levels will be determined by an Immunoassay Kit (LIAISON®).

The inflammation markers IL-1, IL-6, IL-10 and TNF- α , will be determined using ProQuantum High-Sensitivity Immunoassays technique

Diets

As above-mentioned, patients will be randomly allocated to one of two diets for a period of 8 weeks.

NUTRIGENETIC DIET: Weekly, personalized meal plans (menus) will be provided every 2 weeks, prepared based on the anthropometric needs of the patients, with a caloric reduction (-500 kcal). These weekly menus (Sunday to Monday) consist of 5 meal times (breakfast, snack, lunch, snack and dinner). The distribution of the macronutrients: carbohydrates, proteins and fats, as well as the percentages of polyunsaturated, monounsaturated and saturated fatty acids, will be established according to certain nutrigenetic recommendations identified in the reference bibliography.

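### Within-arm paired t-tests stand unranked beside the between-arm tests, so significance in the nutrigenetic arm alone could be misread as superiority over a control diet with the same energy restriction

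*SAP*

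**What the plan says.** The Protocol's Hypothesis is comparative: the nutrigenetic diet "will provide a greater decrease in plasma lipids, inflammatory markers and improvement in body composition, compared to the administration of a standard diet". Under Diets, the nutrigenetic and the conventional plan are described in the same terms on energy, each "with a caloric reduction (-500 kcal" per the respective paragraph. They differ in macronutrient and fatty-acid composition.

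The SAP sizes the trial on the difference between arms in total cholesterol. Its analysis paragraph then lists three approaches in turn:

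- Within arm: "For each treatment group, all markers will be tested using" a paired t-test that compares baseline with the week 4 and week 8 visits.
- Between arms: independent-samples "t tests will be also performed to find possible difference regarding these markers between treatments Nutrigenetic diet and Conventional diet".
- Longitudinal: "a mixed models approach including repeated-measures modeling will be utilized to find possible significant effects of the treatment effect at baseline" on the effect at the two later visits, with confounders that are not named.

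One significance threshold, 0.05, covers everything. No sentence says which analysis decides the hypothesis, and none says that the within-arm tests are descriptive.

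**The concern.** A paired t-test inside one arm asks whether that arm changed from baseline. With the same energy reduction in both arms, and counselling and menus in both, a change from baseline is plausible in each whether or not the genetic tailoring does anything. Such a test therefore says little about the nutrigenetic component.

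The danger lies in setting the two within-arm results side by side. If the nutrigenetic arm crosses 0.05 and the conventional arm just misses it, the pattern looks like superiority. It is not a test of the difference between diets, and it arises often when the diets are equally effective. Because the SAP gives the within-arm tests no subordinate status, a report could rest on that pattern and still appear to follow the plan. The mixed model does not settle the matter, because its stated aim defines no treatment-by-visit contrast.

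**Working it through.** **1. The plan's own figure.** Inputs from the SAP: standardised effect 0.9772364, power 95%, one-tailed two-sample t-test, minimum 24 per arm. With a one-sided 5% level, the exact noncentral-t calculation gives 24 per arm (power 95.4%), so the figure reproduces as a between-arm calculation. It does not reproduce with the printed level of 0.5% (40 per arm one-sided); that is a separate matter.

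**2. Numbers analysed per arm.** 24 is the stated minimum. The recruitment aim of 50 less the stated 30% loss gives 50 × 0.7 = 35. With no losses it is 50.

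**3. Chance that only the nutrigenetic arm is significant when the diets are equal.** Let d be the true mean change divided by the SD of change, the same in both arms. For a two-sided 5% paired t-test with n participants,

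p = P(|T| > t(0.975; n − 1)), where T is noncentral t with n − 1 degrees of freedom and noncentrality d√n.

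The arms are independent, so

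P(nutrigenetic arm only) = p(1 − p).

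Example at n = 24, d = 0.4: noncentrality 0.4 × √24 = 1.96, p = 0.467, and 0.467 × 0.533 = 0.249.

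Example at n = 35, d = 0.5: noncentrality 0.5 × √35 = 2.96, p = 0.820, and 0.820 × 0.180 = 0.148.

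The documents give no SD of change and no expected change within an arm, so d is an assumption and a range is shown. Entries are P(nutrigenetic arm only), per marker and visit:

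| d | n = 24 | n = 35 | n = 50 |
|---|---|---|---|
| 0.2 | 13.1% | 16.6% | 20.3% |
| 0.3 | 20.6% | 24.1% | 24.8% |
| 0.4 | 24.9% | 23.2% | 16.5% |
| 0.5 | 22.7% | 14.8% | 6.2% |
| 0.6 | 15.8% | 6.4% | 1.4% |
| 0.8 | 3.5% | 0.4% | 0.0% |

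**4. Benchmark.** Simulation of 50,000 trials per setting, for d from 0.2 to 0.6, agreed with the formula (24.9% at n = 24, d = 0.4; 14.7% at n = 35, d = 0.5). In the same data a two-sided between-arm t-test on change rejected in 4.8% to 5.1% of trials, so about 2.5% in favour of the nutrigenetic diet.

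**5. How often the opportunity arises.** Leaving out height and dietary intake, the Protocol's dependent variables include 15 body-composition and blood markers. Its measurement sections add VLDL, HOMA-IR, four cytokines and blood pressure, making 15 + 7 = 22. If all count as markers (the SAP does not define the term), there are 22 × 2 visits × 2 arms = 88 within-arm tests.

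**The case against.** The strongest reply is that the SAP does plan the right comparison, for the same markers, in the sentence straight after the within-arm tests, and follows it with a mixed model. That stands. A reader might infer that the investigators intend to conclude superiority from within-arm P values; no sentence says so. A reader might also take the within-arm tests as primary because they come first. Listing order does not make an analysis primary, and both the hypothesis and the sample-size text point to the between-arm contrast.

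The reply only goes so far. The sizing sentence names a variable. It does not fix the visit, the model or the decision rule, and it does not subordinate the within-arm tests.

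The size of the risk can also be overstated. A reader might quote the chance that exactly one arm is significant, 2p(1 − p), which reaches 50%. Half of that is the conventional arm alone, which would not support the hypothesis, so the ceiling for a false claim of nutrigenetic benefit is 25%. The rates also apply only to someone who reads the within-arm results and sets the planned between-arm tests aside. They peak at moderate change and fall quickly at larger change.

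Finally, removing the within-arm P values is partly a matter of preference, since a clear descriptive label would remove most of the risk. That is fair. Confidence intervals carry the same information with less temptation to compare P values across arms.

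**Conclusion.** The concern holds as a risk of misinterpretation from an unranked list of analyses. It is not a missing comparison, and the documents do not show an intention to claim benefit from within-arm tests.

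For equal diets and moderate true change, reading significance in the nutrigenetic arm alone as superiority is wrong roughly five to ten times as often as the direct test in the same direction (13% ÷ 2.5% ≈ 5; 25% ÷ 2.5% = 10). At 0.8 SD the problem largely disappears. With many markers of different kinds, it is plausible that some fall in the moderate range, but the documents do not allow that to be checked.

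The figures assume equal true change in both arms, normally distributed changes and a two-sided 5% level. The SAP's 0.05 threshold states no sidedness, and its sizing is one-tailed. With one-sided 5% tests the direct comparison would err in favour of the nutrigenetic diet 5% of the time, and p(1 − p) would still be capped at 25%.

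**What to change.** Amend the SAP's analysis paragraph in three respects:

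- Report change from baseline within each arm as a mean with 95% CI, described as descriptive only, without P values.
- State that the efficacy conclusion rests on the between-arm difference in total cholesterol at week 8, adjusted for baseline, from either the mixed model (with the treatment-by-visit contrast written out) or ANCOVA. Choose one before the data are examined. Total cholesterol is the variable already used for sizing, and week 8 is the end of the intervention.
- Treat the other markers, and week 4, as secondary between-arm comparisons.

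This changes wording only. Visits, data collection and the stated sample size are untouched. The direct cost is that there are no within-arm P values to report. There is also a decision for the investigators: the hypothesis spans lipids, inflammatory markers and body composition, and naming one deciding contrast gives the others secondary status.
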